4.2 STUDY POPULATION

4.2.1 SAMPLE SIZE CALCULATION

There are no current data available regarding the minimally clinically important differences for MGS nor SPEED scores to inform an effect size. Data from Blackie et al³ show a 12-point improvement in MGS score and 8-point improvement in SPEED scores with small standard deviations, corresponding to very large effect sizes of 1.7 and 1.8, respectively. This data supports a minimum sample of 9 in each group would be required to detect an 8-point mean difference in

SPEED scores at 90% power (alpha=0.05, power analysis = a priori, two-tailed, difference between two independent means).

However, an effect size of 1.7 and 1.8 are ambitious targets in this field. Applying targets of a more realistic effect size of 1.0 and a power of 90%, a minimum sample size of 23 in each group is recommended (alpha=0.05, power analysis = a priori, two-tailed, difference between two independent means). Factoring a 10% dropout, the total suggested sample size is 52 participants.

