4.2.2 NUMBER OF PARTICIPANTS

Participants will be recruited using CORE records and advertising approved by the University of Waterloo Office of Research Ethics. Participants expressing an interest in the study will be pre-screened using the CLDEQ-8 questionnaire to assess whether they meet the symptomatic contact lens wear criteria. However, eligibility for the study can only be determined at the screening visit using the inclusion and exclusion criteria. Data from the pre-screening questionnaire will not be considered as study data and will be confidentially disposed of. This questionnaire will be repeated at the screening visit and stored as study data.

Up to 52 eligible participants will be randomized with a target of 46 participants completing the study. Informed consent will be obtained for all participants prior to their enrolment in the study.

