8 DISCONTINUATION FROM THE STUDY

Participants may be discontinued at the discretion of the investigator or sponsor in consideration of participant safety or protocol compliance, or at discretion of the participant. Participants discontinued from a study will be reimbursed \$20 per hour for their active involvement in the study (including the initial screening visit). Data will not be included in statistical analysis, unless permission is granted by the participant at the time of discontinuation. The following is a list of possible reasons for discontinuation from the study:

- Screening failure: Participants will be discontinued if they do not meet the inclusion and exclusion criteria outlined in section 4.2.3.
- Unacceptable performance with products to be used in study: Participants may be discontinued if they are unable to achieve acceptable comfort and /or vision with the study products.
- Positive slit lamp finding: Participants may be permanently discontinued from the study depending on the severity of the condition and on the judgement of the investigator.
- Adverse event: If a participant experiences an adverse event during the study they may be discontinued based on the clinical judgement of the investigator.
- Symptoms: If the participant has persistent symptoms they may be discontinued based on the clinical judgement of the investigator.
- Disinterest, relocation or illness: The participant may choose to discontinue due to reasons within or beyond their control.
- Violation of protocol or non-compliance: The participant will be discontinued if they are unable or unwilling to follow the protocol specified visit schedules and/or study procedures.
- Instillation of topical ocular medication: The participant will be discontinued if they elect to use a topical ocular medication during the study unless that topical ocular medication is prescribed for a limited duration (less than two weeks) to treat a transient condition; in this case the participant may remain an active participant (at the discretion of the

investigator) after stopping topical ocular medication following resolution of the ocular condition).

- Lost to follow-up: The participant will be discontinued if they cannot be contacted and do not return for a final exit visit, and if the investigator has made a reasonable effort to contact the participant for a final study visit.

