10 STATISTICAL ANALYSIS AND DATA MANAGEMENT

10.1 STATISTICAL ANALYSIS

All data will be analyzed by CORE at the University of Waterloo. Descriptive statistics will be provided on information regarding baseline variables (e.g. age, sex). The appropriate tests will be selected based on tests of normality; non-parametric tests will be used for data not showing a normal distribution. Analysis of variables will be conducted separately on each eye, and data will not be pooled. For assessments conducted for each eye separately, the right eye will be used for analysis if there is no difference between eyes.

The following planned comparisons of the key endpoints (SPEED scores, MGS, pre-lens tear break-up time, reported average wear time and comfortable wear time) will be made:

- Within group comparisons:
 - Baseline vs. 1 month [2-sided paired t-test or Wilcoxon signed rank test]
 - For treatment group only: Baseline vs. 1 month vs. 3 month [Repeated measures ANOVA or Friedman test]
 - Baseline vs. 1 month pooled data (i.e. treatment group and control-treatment group after 1 month treatment) [2-sided paired t-test or Wilcoxon signed rank test]
- Between group comparisons:
 - 1 month post-treatment vs. 1 month control (i.e. no treatment) [2-sided independent t-test or Mann-Whitney U test]

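### The only planned 3-month analysis uses complete cases and, in its ANOVA form, names no sphericity correction; a mixed model would be a cheap improvement to this non-primary, within-arm result

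*Combined protocol and SAP*

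**What the plan says.** Section 10.1 (Statistical analysis) lists the comparisons for five "key endpoints (SPEED scores, MGS, pre-lens tear break-up time, reported average wear time and comfortable wear time". Only one of them extends to 3 months: "For treatment group only: Baseline vs. 1 month vs. 3 month [Repeated measures ANOVA or Friedman test". The other within-group tests compare baseline with 1 month, and the between-group test is at 1 month.

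The choice between the parametric and the rank test follows one rule: "The appropriate tests will be selected based on tests of normality; non-parametric tests will be used for data not showing a normal distribution". No sphericity check, epsilon correction, mixed model, imputation or analysis population is named.

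Two other sections bear on who is analysed:
- Section 4.2.2 expects some loss: "Up to 52 eligible participants will be randomized with a target of 46 participants completing the study".
- Section 8 lists reasons for leaving that include a poor outcome ("Participants may be discontinued if they are unable to achieve acceptable comfort and /or vision with the study products") and says of discontinued participants: "Data will not be included in statistical analysis, unless permission is granted by the participant at the time of discontinuation".

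Section 2 sets both objectives at 1 and 3 months, makes SPEED at 1 month the primary endpoint, and places SPEED at 3 months among the exploratory endpoints.

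**The concern.** A repeated-measures ANOVA and a Friedman test, as normally run, need all three visits from each participant. Someone seen at baseline and 1 month but not at 3 months contributes nothing to this comparison. If the people lost after 1 month are those who improved least, the remaining completers show too large a 3-month change.

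The ANOVA also assumes that the three pairwise differences between visits have equal variance. That may well fail here. Baseline is measured after at least 12 hours without lenses (Section 4.4.2). Both follow-ups are measured after treatment and at least 4 hours of lens wear (Section 4.4.3), so they may correlate more with each other than with baseline. When the assumption fails, the uncorrected F test rejects a true null hypothesis in more than 5% of trials.

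At stake is the 3-month half of the two objectives, because no other planned test covers it.

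**Working it through.** **1. The plan's own figure.** Section 4.2.1 uses an effect size of 1.0 and 90% power with "alpha=0.05, power analysis = a priori, two-tailed, difference between two independent means". The noncentral t calculation gives 22.02, so 23 per group. With 10% dropout, 23 / 0.9 = 25.6, so 26 per group and 52 in total. Both figures reproduce. The plan states no power or error rate for the three-visit test.

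**2. Participants lost to the test.** With 1:1 allocation the treatment group has 26. 26 × 0.9 = 23.4, so about 23 are complete and about 3 drop out of the three-visit comparison.

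**3. Sphericity.** The documents give no correlations or visit SDs, so all values here are assumptions. Take equal SDs, a correlation of 0.3 between baseline and each follow-up, and 0.8 between follow-ups. In SD² units the variances of the pairwise differences are:
- baseline to 1 month, and baseline to 3 months: 2(1 − 0.3) = 1.4
- 1 month to 3 months: 2(1 − 0.8) = 0.4

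The variances of the two orthonormal contrasts are λ₁ = (6 − 4×0.3 − 4×0.3 + 2×0.8)/6 = 0.867 and λ₂ = 1 − 0.8 = 0.2. Then ε = (λ₁ + λ₂)² / [2(λ₁² + λ₂²)] = 1.138 / 1.582 = 0.72, where 1 means that sphericity holds.

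**4. Type I error of the uncorrected ANOVA**, nominal 5%, from 60,000 simulated data sets per row:

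| Assumed structure | ε | n = 23 | n = 26 |
|---|---|---|---|
| All correlations 0.5 | 1.00 | 5.2% | 5.1% |
| Adjacent visits 0.5, baseline to 3 months 0.25 | 0.93 | 5.3% | 5.4% |
| SDs rising 1 / 1.3 / 1.6 (correlations 0.6, 0.3, 0.6) | 0.82 | 5.9% | 5.9% |
| Baseline 0.3, follow-ups 0.8 | 0.72 | 6.5% | 6.7% |
| Baseline 0.3, follow-ups 0.9 | 0.61 | 7.5% | 7.5% |
| Exact bound | 0.50 | 8.7% | 8.7% |

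A second set of simulations (40,000 data sets per structure, n = 23) reached 7.7% at ε of 0.60 to 0.63. The bound is P(F(1, 22) > F₀.₉₅(2, 44)) = P(F(1, 22) > 3.209) = 8.7%. With a Greenhouse-Geisser correction the rate is 4.6% to 5.1% throughout. The Friedman test gives 4.6% to 5.1%, and 5.4% to 5.5% in a near-worst case.

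**5. Completer bias at 3 months.** Assume a true SPEED change of −4.5, an SD of 4.4 at each visit, and that the 3 of 26 with the worst 1-month scores leave before month 3. The lost fraction is f = 3/26 = 0.115, with normal cut-point z = 1.198 and density φ(z) = 0.195. To a close approximation:

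bias = (r between follow-ups − r baseline to follow-up) × φ(z)/(1 − f) × SD = (difference in r) × 0.220 × 4.4

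| r baseline to follow-up | r between follow-ups | Bias by formula (points) | Simulated completer change |
|---|---|---|---|
| 0.5 | 0.5 | 0.0 | −4.5 |
| 0.3 | 0.5 | 0.19 | −4.7 |
| 0.3 | 0.7 | 0.39 | −4.9 |
| 0.3 | 0.8 | 0.48 | −4.95 |
| 0.3 | 0.9 | 0.58 | −5.05 |

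If the 3 are lost at random, the completer change is −4.5 in every row. A likelihood estimate that uses all observed visits also stays at about −4.5. The standard error of the completer change is about 1 point.

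**The case against.** Most of the case on the other side limits the size of the point, and much of it stands.

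- **The 1-month results.** A reader might infer that early leavers distort the 1-month findings too. The documents do not support that: Section 10.1 has separate paired and between-group tests at 1 month, which keep anyone who misses only month 3, subject to Section 8.
- **Who leaves.** A reader might infer that leavers will be the poor responders. Section 8 also lists disinterest, relocation, illness, non-compliance and loss to follow-up. Outcome-related loss is foreseeable, not established. Even when the worst responders leave, the 3-month bias vanishes if all correlations are equal.
- **Sphericity.** SPEED is not an eligibility criterion, so selection on entry thresholds does not by itself show a sphericity failure for it. The 7% to 8% rates need a follow-up correlation near 0.9. With a 4.5-point change, SD 4.4 and n = 23, corrected and uncorrected tests disagreed in only 0.1% to 1.5% of simulated trials, and in 2% to 8% with half that change.
- **The remedy.** A mixed model alone does not bring leavers back, because Section 8 removes their data unless they give permission. Anyone lost before month 1 has no follow-up and stays out in any case. A normal-theory model as the main analysis also departs from the plan's non-parametric rule, so the plan would have to say how the two fit.

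These limits rule out calling this a serious flaw. They do not show that the planned method is the better one: the plan has no other 3-month analysis, no missing-data rule and no correction.

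**Conclusion.** The point holds as a cheap improvement. The planned 3-month test uses about 23 of 26 treated participants at the planned loss, and its ANOVA form has a type I error of about 5% to 7.7% under the assumed correlations, never above 8.7%. The Friedman form is near nominal. The 3-month SPEED change would be overstated by about 0.2 to 0.6 points on a 0 to 28 scale if the losses after month 1 are the worst responders and the follow-ups correlate more with each other than with baseline. The overstatement is zero if loss is random.

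The correlations, the SD of 4.4, the change of 4.5 points and the loss pattern are all assumptions. The analysis is within one arm; SPEED at 3 months is exploratory, while the other endpoints sent through this test are secondary. The documents do not support reading this as a threat to the primary 1-month comparison or the sample size.

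**What to change.** In Section 10.1, replace the three-visit line with a mixed model for repeated measures in the treatment group: visit as a categorical factor, unstructured covariance, Kenward-Roger degrees of freedom. Include every treatment-arm participant who has a baseline and at least one follow-up and whose data may be used. Report the baseline-to-3-month change with a 95% CI.

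Keep the ANOVA with a Greenhouse-Geisser correction, or the Friedman test where normality fails, as a supporting analysis. Add a sentence saying how this fits the rule that non-normal data go to non-parametric tests.

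In the same edit, reconcile Section 10.1 with Section 8 so that the analysis set is clear, for example by routinely asking those who discontinue for permission to use data already collected.

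The cost is a few sentences across the two sections and slightly more analysis work, with no extra participants or visits. The downside is that the model assumes missing at random, meaning that loss depends only on scores already observed; the plan should state this.

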2 OBJECTIVES

The objectives of this clinical trial are:

- To assess eye dryness symptoms (using the SPEED questionnaire) at 1- and 3-months post iLux® treatment;
- To assess Meibomian gland secretions (by expression using the Meibomian Gland Evaluator) at 1- and 3-months post iLux® treatment.

Primary endpoint:

- Changes in SPEED questionnaire score at 1 month.

Secondary endpoints:

- Meibomian gland secretion (assessments will be reported as meibomian gland scores (MGS));
- Pre-lens tear break-up time;
- Reported average wear time and comfortable wear time.

Exploratory endpoint:

- Changes in symptoms, determined using CLDEQ-8 and OSDI questionnaires, at 1- and 3-months, and SPEED at 3 months post iLux® treatment.

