3 NULL HYPOTHESES

- There will be no difference between treatment and control groups for mean comfortable CL wear time.
- There will be no difference between treatment and control groups for symptoms, determined using SPEED questionnaire, at 1-month.
- There will be no difference between treatment and control groups for Meibomian gland score (MGS) at 1-month.

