4.2.3 INCLUSION AND EXCLUSION CRITERIA

A person is eligible for inclusion in the study if he/she:

1. Is at least 18 years of age and has full legal capacity to volunteer;
2. Has read and signed an information consent letter;
3. Is willing and able to follow instructions and maintain the appointment schedule;
4. Has been using the same CL type (brand, material and dimensions) for > 3 months;
5. Wears commercially available soft CLs on average >2 hours per day, 4-7 days per week;
6. Is willing to try to wear their habitual CLs on average \geq 6 hours per day, 4-7 days per week and maintain this for the duration of their involvement in the study;
7. Demonstrates an acceptable lens fit of their habitual contact lenses;
8. Does not have contact lens discomfort due to contact lens fit, lens material or known solution compatibility issues, in the opinion of the investigator;
9. Has at least one month supply of their habitual contact lens products at the time of the screening visit;
10. Has a CLDEQ-8 score \geq 12;

11. Has dry eye symptoms without CL wear (OSDI \geq 13) and has at least one of the two following signs:
 - a. Non-invasive tear break-up time (NITBUT) of < 10 seconds in at least one eye;
 - b. Fluorescein staining: > 5 spots of corneal staining OR > 9 conjunctival spots OR lid wiper staining (\geq 2mm length, \geq 25% width) in at least one eye;
12. Has a lipid layer thickness of \leq 100 nm in both eyes;
13. A meibomian gland secretion score (MGS) of \leq 15 for 15 glands of the lower lid in both eyes.

A person will be excluded from the study if he/she:

1. Is participating in any concurrent clinical or research study;
2. Has used any prescription systemic medications or topical treatments for MGD or dry eye for the past 30 days prior to the screening visit and not willing to stop using these for the study duration (excluding over-the-counter artificial tears, dietary supplements and ocular lubricants but includes warm compresses, eyelid massage, eyelid hygiene, manual meibomian gland expression, punctal plug insertion or punctal occlusion, intense pulsed light treatment of the face or eyelids);
3. Has previously received treatment with an eyelid thermal pulsation device;
4. Has a history of any of the following ocular (eye or eyelid) conditions or procedures in either eye within the past 90 days prior to the screening visit:
 - a. Ocular trauma
 - b. Chemical burns
 - c. Ocular *Herpes simplex* or *Herpes zoster* infection

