4.5.3.2 SPEED

The Standard Patient Evaluation of Eye Dryness (SPEED) questionnaire (TearScience, Morrisville, NC) is a dry eye questionnaire developed to assess the frequency (0-3 scale) and severity (0-4 scale) of patient symptoms and reviews the presence of symptoms within the past 72 hours and past 3 months.⁷ Scores range from 0-28, with higher values indicating more severe dryness.

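### The primary endpoint is worded as a change in SPEED, but the only between-group test uses 1-month values without baseline and no comparison is labelled primary; a named ANCOVA would settle this at almost no cost (optional)

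*Combined protocol and SAP*

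**What the plan says.** Section 2 (Objectives) gives the primary endpoint as "Changes in SPEED questionnaire score at 1 month". It does not say whether the change is judged within a group or between groups.

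Section 3 states the SPEED null hypothesis as a contrast between groups: "There will be no difference between treatment and control groups for symptoms, determined using SPEED questionnaire, at 1-month". It is the second of three nulls and is not marked primary.

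Section 4.2.1 sizes the trial for a difference between two independent means, using "a more realistic effect size of 1.0 and a power of 90%, a minimum sample size of 23 in each group is recommended". It does not say whether the effect size is in units of the 1-month SD or of the SD of change.

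Section 10.1 lists planned comparisons for five key endpoints together. Three are within-group, and these are the only place where baseline enters. One is between-group: "1 month post-treatment vs. 1 month control (i.e. no treatment) [2-sided independent t-test or Mann-Whitney U test". The choice of test follows a general rule: "The appropriate tests will be selected based on tests of normality; non-parametric tests will be used for data not showing a normal distribution". No comparison is called primary, and no adjusted model appears.

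Section 4.4.2 has every participant complete SPEED at Visit 1, before randomisation.

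**The concern.** Two things are left loose.

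First, the endpoint wording and the test do not match. A reader of section 2 expects an analysis of change, but section 10.1 compares groups on 1-month values only. The listed analysis that literally examines change in SPEED is the paired comparison of baseline with 1 month within a group. That comparison ignores the randomised control. It would mix any treatment effect with regression to the mean after selection on symptoms ("Has dry eye symptoms without CL wear" is part of entry, alongside a CLDEQ-8 threshold). It would also absorb the switch from at least 12 hours without lenses at Visit 1 to at least 4 hours of wear at the 1-month visit. Both arms share these influences at 1 month, so the between-group contrast is protected from them.

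Second, a baseline measure of the primary outcome is collected from everyone and then not used in the between-group analysis. If it correlates with the 1-month score, precision is given away.

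**Working it through.** **Inputs.** From section 4.2.1: two-sided alpha 0.05, effect size d = 1.0, 90% power, 23 per arm. Assumed, because the documents do not give them: r, the correlation between Visit 1 and 1-month SPEED (range 0 to 0.7); roughly normal scores with equal SD at both visits; d in 1-month SD units.

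**1. The plan's own figure.** For a two-sample t-test the noncentrality is d·√(n/2) = 1.0 × √(23/2) = 3.391, with 44 degrees of freedom and critical value 2.015. Power is 91.2%. With 22 per arm it is 89.97%, so 23 reproduces. Then 46/0.9 = 51.1, which rounds up to the stated 52. The planned sample size therefore belongs to the unadjusted test of 1-month values.

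**2. ANCOVA on Visit 1 SPEED.** The variance of the adjusted difference is σ²(1 − r²)(2/n + D²/S), where D is the chance baseline difference between arms and S the pooled within-arm sum of squares at baseline. On average this is (2σ²/n)(1 − r²)(1 + 1/42). There are 43 degrees of freedom, critical value 2.017.

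**3. Unadjusted change score.** Its SD is σ√(2(1 − r)), so the effect size becomes d/√(2(1 − r)): 0.707, 0.845, 1.000 and 1.291 at r = 0, 0.3, 0.5 and 0.7.

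Power at d = 1.0, 23 per arm:

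| r | 1-month values (planned) | ANCOVA | Change score |
|---|---|---|---|
| 0 | 91.2% | 90.6% | 65.0% |
| 0.3 | 91.2% | 93.0% | 80.0% |
| 0.5 | 91.2% | 96.6% | 91.2% |
| 0.7 | 91.2% | 99.6% | 99.0% |

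**4. In SPEED points.** Section 4.2.1 reports an "8-point improvement in SPEED scores with small standard deviations, corresponding to very large effect sizes of 1.7 and 1.8, respectively". If that effect size used an ordinary score SD, which the text does not say, the SD is 8/1.8 = 4.44. The planned 95% CI half-width is 2.015 × √(2/23) × 4.44 = 2.64 points. Multiplying by √((1 − r²)(1 + 1/42)) × 2.017/2.015 gives 2.67, 2.55, 2.32 and 1.91 points for ANCOVA at r = 0, 0.3, 0.5 and 0.7.

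**5. Do the two between-group readings agree?** In simulation with normal scores and d = 1.0, the 1-month-value and change-score t-tests disagree on significance in about 19%, 12% and 9% of trials at r = 0.3, 0.5 and 0.7. Repeat runs differ by about a point. With no effect, at least one of the two is significant in about 8.3% to 9.5% of trials.

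**6. Sensitivity to the SD unit.** If d = 1.0 is in change-SD units, the effect in 1-month SD units is √(2(1 − r)), that is 1.183, 1.000 and 0.775 at r = 0.3, 0.5 and 0.7. The planned test then has 97.5%, 91.2% and 72.9% power, and the change score has 91.2% throughout.

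**7. Sensitivity to shape.** In simulations with strongly skewed scores (gamma, skewness 1.4), the plan's normality rule picks Mann-Whitney in about 84% of trials and the planned approach has about 95% power at d = 1.0. Raw-score ANCOVA has 92.3% at r = 0.3 and 95.6% at r = 0.5, breaking even at r of about 0.47 to 0.49. Rank ANCOVA has 96.8% and 98.4%. Nothing in the documents says SPEED will be this skewed. Whole-number scores on the 0–28 scale with mean 10 or 14 behave within a point of the normal case.

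**The case against.** The strongest reply is that the intended test is already clear. Section 3 states the SPEED null between groups at 1 month, section 4.2.1 sizes for two independent means, and section 10.1 lists exactly one between-group comparison, on scores. No between-group change-score test is planned anywhere, and section 2 uses the word change loosely for its exploratory symptom endpoint too. This largely stands. The between-group 1-month contrast is evidently what is meant, and the remaining gap is that no section calls it primary while the endpoint wording points elsewhere.

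A reader might infer that the planned test is biased or underpowered. The documents do not support that: randomisation makes the unadjusted comparison valid, simulated type I error is about 5%, and the stated sample size meets its own target under the 1-month SD reading.

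A reader might also infer that the plan carries a false-positive rate of 9%. It does not. That figure is a ceiling, reached only if an analyst left the plan, ran an unlisted change-score test and reported whichever result was significant.

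Finally, the gain from ANCOVA rests on an unknown r, and even the direction of the influences on r is unclear. Entry thresholds and the change in lens-wear state may lower it. SPEED's recall window may raise it, since the questionnaire "reviews the presence of symptoms within the past 72 hours and past 3 months". That objection limits how much gain can be promised; it does not make the adjustment costly.

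**Conclusion.** The point holds as an optional, near-free improvement. The mismatch between endpoint wording and test, and the lack of a labelled primary comparison, are on the page and depend on no assumption. The precision gain is conditional. With roughly normal scores and d = 1.0 in 1-month SD units, ANCOVA changes power from 91.2% to between 90.6% (r = 0) and 99.6% (r = 0.7). The same adjustment would avoid the weakness of a change score at low r, where power falls to 65.0%. The sample size of 52 need not change. Confidence is medium, because r, the shape of the SPEED scores and the SD unit behind the effect size are all unstated.

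**What to change.** In section 10.1, name one primary analysis: ANCOVA of 1-month SPEED (Visit 3A in the treatment group versus Visit 2B in the control-treatment group) on randomised group, with Visit 1 SPEED as covariate. Report the adjusted mean difference with its 95% CI, and do not let a normality test choose this analysis. Pre-state rank ANCOVA as the sensitivity analysis. Label the within-group tests supportive. Align sections 2, 3 and 10.1, for example as SPEED at 1 month adjusted for Visit 1 SPEED, and state in section 4.2.1 which SD the effect size refers to.

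The cost is wording only, with no new data, visits or participants. The statistical cost is one degree of freedom and less than 1 power point if r is near 0 and scores are roughly normal. If SPEED proves strongly skewed, raw-score ANCOVA can have less power than Mann-Whitney unless r is moderate, which is why the rank version is fixed in advance.
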